Cohort 2: In another 3 patients, the dose of CPI-613 for the 3-weeks-on-1-week-off treatment cycles will be as determined from Cohort 1. These patients will also be treated with the 5 daily doses of CPI-613 during the pre-Cycle 1 week. The dose of CPI-613 for the pre-Cycle 1 week will be 1,200 mg/m²/day, which has previously been established to be the weekly MTD (see Section 6.1.2). If none of these 3 patients develop a DLT, the study can move onto Cohort 3.

However, if a DLT is observed in a patient (whether it is the 1st, 2nd or 3rd of the 3 intended patients), the number of patients in this cohort will be expanded to a maximum of 6 patients. If no DLT is observed in another patient out of a maximum of 6 patients, the study will move onto Sub-Cohort 2 (see below). However, if a DLT is observed in 2 patients, no additional patients will be treated at 1,200 mg/m²/day during the pre-Cycle 1 week even though the total number of patients at this cohort is as few as 2. The dose level of 1,200 mg/m²/day during the pre-Cycle 1 week, which induces a DLT in 2 or more patients, is considered to be above the MTD for the pre-Cycle 1 week. In this case, the dose of CPI-613 for the pre-Cycle 1 week in subsequent patients in this trial will be 600 mg/m²/day (or 3,000 mg/m²/week, equivalent to the MTD when given as a single dose).

Sub-Cohort 2: Sub-Cohort 2 is activated only if 1 out of 6 patients exhibits DLT in Cohort 2. There are 3 patients in this sub-cohort, the dose of CPI-613 for the 3-weeks-on-1-week-off treatment cycles will be as determined from Cohort 1. These patients will also be treated with the 5 daily doses of CPI-613

Comprehensive Cancer Center of Wake Forest University
A Pilot Study: Open-Label Clinical Trial of CPI-613 in Patients with Advanced Bile Duct
Cancers
CCCWFU # 59212

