during the pre-Cycle 1 week. The dose of CPI-613 for the pre-Cycle 1 week will be 1,700 mg/m²/day. If none of these 3 patients develop a DLT, the study can move onto Cohort 3. However, if a DLT is observed in a patient (whether it is the first, second or third of the 3 intended patients), the number of patients in this cohort will be expanded to a maximum of 6 patients. If no DLT is observed in another patient out of a maximum of 6 patients, the study will move onto Cohort 3. However, if a DLT is observed in 2 patients, no additional patients will be treated at 1,700 mg/m²/day during the pre-Cycle 1 week even though the total number of patients at this sub-cohort is as few as 2. The dose level of 1,700 mg/m²/day during the pre-Cycle 1 week, which induces a DLT in 2 or more patients, is considered to be above the MTD for the pre-Cycle 1 week. In this case, the dose of CPI-613 for the pre-Cycle 1 week in subsequent patients in this trial will be 600 mg/m²/day (or 3,000 mg/m²/week, equivalent to the MTD when given as a single dose).

Cohort 3: This cohort will be performed only if DLT is observed in Cohort 2, or DLT is observed in 1 or less patients in Sub-Cohort 2. There are 3 patients in this cohort, and the dose of CPI-613 for the 3-weeks-on-1-week-off treatment cycles will be as determined from Cohort 1. The dose for the 5 daily IV infusions during the pre-Cycle 1 week will be 2,300 mg/m²/day. If none of these 3 patients develop a DLT, the study can move onto Cohort 4. However, if a DLT is observed in a patient (whether it is the 1st, 2nd or 3rd of the 3 intended patients), the number of patients in this cohort will be expanded to a maximum of 6 patients. If no DLT is observed in another patient out of a maximum of 6 patients, the study will move onto Cohort 4. However, if a DLT is observed in 2 patients, no additional patients will be treated at 2,300 mg/m²/day during the pre-Cycle 1 week even though the total number of patients at this sub-cohort is as few as 2. The dose level of 2,300 mg/m²/day during the pre-Cycle 1 week, which induces a DLT in 2 or more patients, is considered to be above the MTD for the pre-Cycle 1 week. In this case, the dose of CPI-613 for the pre-Cycle 1 week in subsequent patients in this trial will be 1,700 mg/m²/day.

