Cohort 4: This cohort will be performed only if DLT is observed in 1 or less patients in Cohort 3. There are 3 patients in this cohort, and the dose of CPI-613 for the 3-weeks-on-1-week-off treatment cycles will be as determined from Cohort 1. The dose for the 5 daily IV infusions during the pre-Cycle 1 week will be 3,000 mg/m²/day. If none of these 3 patients develop a DLT, the study can move onto Cohort 5. However, if a DLT is observed in a patient (whether it is the first, second or third of the 3 intended patients), the number of patients in this cohort will be expanded to a maximum of 6 patients. If no DLT is observed in another patient out of a maximum of 6 patients, the study will move onto Cohort 5. However, if a DLT is observed in 2 patients, no additional patients will be treated at 3,000 mg/m²/day during the pre-Cycle 1 week even though the total number of patients at this cohort is as few as 2. The dose level of 3,000

Comprehensive Cancer Center of Wake Forest University
A Pilot Study: Open-Label Clinical Trial of CPI-613 in Patients with Advanced Bile Duct
Cancers
CCCWFU # 59212

mg/m²/day during the pre-Cycle 1 week, which induces a DLT in 2 or more patients, is considered to be above the MTD for the pre-Cycle 1 week. In this case, the dose of CPI-613 for the pre-Cycle 1 week in subsequent patients in this trial will be 2,300 mg/m²/day

Cohort 5: This cohort is performed once the dose of CPI-613 for the 3-weeks-on-1-week-off treatment cycles has been determined from Cohort 1, and once the dose of CPI-613 for the pre-Cycle 1 week has been determined from Cohort 2-4. There are 10 patients in this cohort. These patients will be treated with CPI-613 for 5 days during the pre-Cycle 1 week at doses as determined from Cohorts 2-4, and the dose of CPI-613 for the 3-weeks-on-1-week-off treatment cycles will be as determined from Cohort 1.

6.1.2 *Justification of the Dose*

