Based on Phase I trials in patients with solid tumors and hematologic malignancies, 3,000 mg/m² is the MTD, when CPI-613 is given as a single agent infused over 2 hours on Days 1 and 4 for 3 weeks of a 4-week treatment cycle. CPI-613 did not induce any significant adverse effects at or below MTD. Additionally, CPI-613 at or below 3,000 mg exhibits anti-tumor activities in patients with various types of solid and hematologic malignancies (Pardee et al, 2011a and b, & 2012; Lee et al. 2011 & 2012; Senzer et al 2012). Because of the safety and efficacy against other cancers, 3,000 mg/m² is the target dose for this pilot study.

In this study, patients will be treated with CPI-613 for 5 consecutive days during pre-Cycle 1, prior to being treated with CPI-613 given 2x weekly for 3 weeks. A sub-MTD (2,300 mg/m², approx. three-quarters of the MTD) will be used in the first 3 patients (in Cohort 1) who will be treated with the 4-week treatment cycles and without treatment during the pre-Cycle 1 week to ensure safety, before initiating the dose escalation procedure to determine the MTD. The maximum plasma concentration (C_{max}) of CPI-613 associated with the dose level of 2,300 mg/m² is ~90 µM, which is significantly lower than the C_{max} of ~200 µM associated with 3,000 mg/m². Therefore, 2,300 mg/m² is expected to be a safe starting dose.

After determining the dose to be used in 3-weeks-on-1-week-off cycles, the safety of the dailyx5 treatment with CPI-613 during pre-Cycle 1 will be evaluated in a dose-escalated manner in Cohorts 2-4.

6.2 Dosing Delay and Dose Modification of CPI-613 in the Event of Adverse Events

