9.0 STATISTICAL CONSIDERATIONS

This is a pilot study with the primary goal to be able to determine initial estimates of RR, and secondary goals to determine PFS and OS. Data from this trial will also provide additional data concerning the safety profile of the CPI-613 therapy. Since there is some uncertainty about what dose to examine for the 10 patients in this pilot study we propose the following pre-defined dose escalation scheme in order to determine the appropriate dose to provide to 10 patients with advanced bile duct cancers. This scheme has been discussed/proposed by the FDA and it is very specific and is described below. The dose-escalation scheme is based on the number of patients exhibiting dose-limiting toxicity (DLT), and DLT is defined as toxicity of Grade 3 or higher. The DLT determining period for all cohorts in the dose-escalation scheme is through the first cycle. Note – this section is redundant with section 6.1 but is included for completeness.

Cohort 1: The first 3 patients will not be treated with the 5 daily doses of CPI-613 during the pre-Cycle 1 week, and will only be treated with 3-weeks-on-1-week-off treatment cycles (see Table 6-1). The dose of CPI-613 will be 2,300 mg/m² (which is approximately three-quarters of the target dose). If none of these 3 patients develop a dose-limiting toxicity (DLT) through Cycle 1, the dose for the 3-weeks-on-1-week-off treatment cycles will be 3,000 mg/m² in all subsequent patients in this trial. However, if a DLT is observed in a patient (whether it is the 1st, 2nd or 3rd of the 3 intended patients), the number of patients in this cohort will be expanded to a maximum of 6 patients. If no DLT is observed in another patient out of a maximum of 6 patients, the dose for the 3-weeks-on-1-week-off treatment cycles will be 3,000 mg/m² in all subsequent patients in this trial. However, once DLT is observed in 2 patients, no additional patients will be treated at 2,300 mg/m² for the 3-weeks-on-1-week-off treatment cycles from that point on, even though the total number of patients in this cohort is as few as 2. The dose level of 2,300 mg/m², which induces a DLT in 2 or more patients, is considered to be above the maximum tolerated dose (MTD) for the 3-weeks-on-1-week-off treatment cycles. In this case, all subsequent patients in this trial will be treated at 1,700 mg/m² for the 3-weeks-on-1-week-off treatment cycles.

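### The Cohort 3 entry condition (Sections 6.1.1 and 9.0) appears to have lost the word *no*: as written it bars escalation after 0/3 DLTs in Cohort 2, where the Cohort 2 rule allows it

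*Combined protocol and SAP*

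**What the plan says.** All the rules below are in Section 6.1.1 and are repeated in Section 9.0, which states that "this section is redundant with section 6.1 but is included for completeness".

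- **Cohort 2** (pre-Cycle 1 dose 1,200 mg/m²/day). After 0/3: "If none of these 3 patients develop a DLT, the study can move onto Cohort 3". After one DLT the cohort expands to at most 6, and 1/6 leads to Sub-Cohort 2. After two DLTs dosing at this level stops and "the dose of CPI-613 for the pre-Cycle 1 week in subsequent patients in this trial will be 600" mg/m²/day.
- **Sub-Cohort 2** (1,700 mg/m²/day). "Sub-Cohort 2 is activated only if 1 out of 6 patients exhibits DLT in Cohort 2". With at most one DLT here the study goes to Cohort 3. With two, the level stops and the dose falls to 600 mg/m²/day.
- **Cohort 3** (2,300 mg/m²/day). "This cohort will be performed only if DLT is observed in Cohort 2, or DLT is observed in 1 or less patients" in Sub-Cohort 2.
- **Cohort 4** (3,000 mg/m²/day). "This cohort will be performed only if DLT is observed in 1 or less patients in Cohort 3".
- **Cohort 5** (10 patients) starts "once the dose of CPI-613 for the pre-Cycle 1 week has been determined from Cohort 2-4".

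Section 6.1.2 adds that the safety of the five daily doses "will be evaluated in a dose-escalated manner in Cohorts 2-4".

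**The concern.** The Cohort 3 condition makes toxicity in Cohort 2 a ground for escalating, and so excludes the cleanest result, 0/3. The Cohort 2 paragraph says the opposite for that result. The permissive *can* in the Cohort 2 rule does not reconcile them, because an *only if* condition forbids what *can* permits.

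This is an operative dosing rule, not background text. Followed as written, escalation ends after 1,200 mg/m²/day. Following the Cohort 2 rule, the next patients receive 2,300 and possibly later 3,000 mg/m²/day. The ten Cohort 5 patients are the analytic sample, so the choice can change the dose at which response rate is estimated. If escalation did end after 0/3, no sentence says what pre-Cycle 1 dose Cohort 5 would receive. The only dose that a Cohort 2 result itself fixes for later patients is 600 mg/m²/day, and that is tied to two DLTs.

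**Working it through.** **1. The plan's own accrual range.** Section 9.0 gives 16 to 40 patients in total, with 16 to 22 most likely. With full cohorts these are 3 + 3 + 10 = 16 at the bottom and 5 × 6 + 10 = 40 at the top (1/6 in each of Cohorts 1, 2, Sub-Cohort 2, 3 and 4). The path with no DLT anywhere gives:

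- under the Cohort 2 rule: 4 × 3 + 10 = 22
- under the Cohort 3 condition as written: 2 × 3 + 10 = 16

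Both totals lie in the most likely range and the maximum of 40 is the same, so the accrual figures do not show which reading was meant.

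**2. Branch check.** Each result of Cohort 2 and Sub-Cohort 2 is set against the entry condition.

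| Result | Do the Cohort 2 and Sub-Cohort 2 rules open Cohort 3? | Condition met as written? | Met if an unopened Sub-Cohort 2 counts as at most one DLT? | Met with *no* inserted? |
|---|---|---|---|---|
| 0/3 in Cohort 2 | yes | **no** | yes | yes |
| 1/6, then at most 1 in Sub-Cohort 2 | yes | yes | yes | yes |
| 1/6, then 2 or more in Sub-Cohort 2 | no | yes | yes | no |
| 2 or more in Cohort 2 | no | yes | yes | no |

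(The last column takes the second limb to apply only when Sub-Cohort 2 has been opened.)

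In the last two rows a *yes* in the third column is not a conflict. *Only if* states a necessary condition, and the explicit stop with the 600 mg/m²/day fallback still governs. The strict conflict is therefore 1 branch of 4 as written and 0 of 4 with *no*. The reading in the fourth column removes the conflict, but the condition is then met on all four branches and restricts nothing.

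**3. How often the affected branch is reached.** The documents give no DLT rate, so p (the per-patient rate in Cohort 2) is assumed, with independent patients and one rate within the cohort.

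- P(0/3) = (1−p)³
- P(1/6) = 3p(1−p)² × (1−p)³ = 3p(1−p)⁵
- With s the chance that Sub-Cohort 2 passes, the share of Cohort 3 openings that come through 0/3 is (1−p)³ / [(1−p)³ + 3p(1−p)⁵s] = 1 / [1 + 3p(1−p)²s]

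| p | P(0/3) | Share through 0/3 at s = 1 |
|---|---|---|
| 5% | 0.857 | 0.881 |
| 10% | 0.729 | 0.805 |
| 20% | 0.512 | 0.723 |
| 30% | 0.343 | 0.694 |

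The share is smallest at s = 1 and p = 1/3, where 3 × (1/3) × (2/3)² = 4/9 and the share is 1/(1 + 4/9) = 9/13 = 0.692. So at least 69% of the trials that the Cohort 2 and Sub-Cohort 2 rules send to Cohort 3 arrive through 0/3, whatever the DLT rates at 1,200 and 1,700 mg/m²/day.

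**The case against.** The strongest reply is that the intent is plain. The Cohort 2 paragraph states the action after 0/3, the Cohort 4 gate depends on low toxicity, and Section 6.1.2 plans escalation across Cohorts 2 to 4. A clinician who met the sentence would see a slip and query it, so a halt is possible rather than established. That stands, and it limits the severity. It does not remove the contradiction, because nothing gives the Cohort 2 sentence precedence.

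The percentages describe how often the branch occurs, not harm, and rest on assumed rates. That also stands. They show only that the fault lies on the main route to Cohort 3.

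One could count an unopened Sub-Cohort 2 as having at most one DLT. As shown above, that empties the condition. On the same strained reading the corrected sentence would still be met after two DLTs in Cohort 2, but the stop rule governs there.

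The version dates run from December 2012 to July 2018, and accrual to target was expected within two years, so escalation may have been finished by this version. The documents do not say.

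Section 9.0 is a declared repeat of Section 6.1. Its identical wording is a second place to correct, not independent evidence of intent. It does make a PDF-extraction fault unlikely.

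**Conclusion.** The concern holds. The entry condition for Cohort 3 contradicts the Cohort 2 rule on the 0/3 branch, and only there. That branch has probability 34% to 86% over assumed DLT rates of 30% down to 5%, and it supplies at least 69% of the intended entries to Cohort 3, given independent patients with one DLT rate within Cohort 2. That a *no* was lost is an inference, though a well-supported one; the contradiction itself can be read directly from the text. No stop rule is weakened and no toxic dose is authorised. It should be corrected because it is an operative escalation rule that is wrong on the branch with no toxicity.

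**What to change.** In the Cohort 3 paragraph of both Section 6.1.1 and Section 9.0, insert *no* before the first *DLT*. Cohort 3 then opens only after no DLT in Cohort 2, or after at most one patient with a DLT in Sub-Cohort 2. This agrees with the existing Cohort 2 and Sub-Cohort 2 rules on all four branches. The cost is one word in two places, with no added patients or procedures.

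### If 1,200 mg/m²/day clears at 0/3 and 2,300 then fails, the final ten patients get 1,700 daily x5, a dose nobody on that path has received

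*Combined protocol and SAP*

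**What the plan says.** Section 6.1.1 sets the Pre-Cycle 1 (daily x5) dose in steps, and Section 9.0 repeats the scheme.

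- Cohort 2 gets 1,200 mg/m²/day, a dose "which has previously been established to be the weekly MTD". After 0/3 DLTs: "If none of these 3 patients develop a DLT, the study can move onto Cohort 3", which is set at 2,300.
- The only daily x5 cohort at 1,700 is Sub-Cohort 2, and "Sub-Cohort 2 is activated only if 1 out of 6 patients exhibits DLT in Cohort 2".
- If Cohort 3 has two DLTs: "In this case, the dose of CPI-613 for the pre-Cycle 1 week in subsequent patients in this trial will be 1,700" mg/m²/day. Nothing makes this depend on 1,700 having been tested.
- If Sub-Cohort 2 has two DLTs: "In this case, the dose of CPI-613 for the pre-Cycle 1 week in subsequent patients in this trial will be 600" mg/m²/day. The same 600 applies if Cohort 2 itself fails.
- The Cohort 3 paragraph opens with "This cohort will be performed only if DLT is observed in Cohort 2", or if at most one DLT occurs in Sub-Cohort 2.
- For Cohort 5, "There are 10 patients in this cohort", at the dose found in Cohorts 2-4. No cohort-level DLT rule is given for it.

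Section 6.1.2 says that "the safety of the dailyx5 treatment with CPI-613 during pre-Cycle 1 will be evaluated in a dose-escalated manner in Cohorts 2-4". Section 9.0 (Accrual Rate and Proposed Analyses) describes the final ten as treated at the MTD.

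**The concern.** A fallback dose should be one that has already passed the DLT rule. The Cohort 4 fallback (2,300) always has. The Cohort 3 fallback has only if Sub-Cohort 2 was run. On the 0/3 path it was not, so ten patients take a dose between a cleared and a failed one, without the three-to-six-patient check given to each of the escalation doses. That conflicts with the statement in Section 6.1.2 and with the MTD description in Section 9.0.

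These ten patients are the analytic sample. The response rate, its confidence interval and the toxicity table by grade are all reported for them, and a reader would take the dose as established by the escalation.

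**Working it through.** **Plan's own totals.** Five cohorts of at most 6 give 30, plus 10 = 40. Three patients each in Cohorts 1 and 2 give 6, plus 10 = 16. With no DLT at all, 3+3+3+3+10 = 22. These reproduce the stated 16-40 and the top of the 16-22 range called most likely. (If Cohorts 1 and 2 both stop after two DLTs in two patients, the total is 14.)

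**Which paths count.** The Cohort 2 text sends 0/3 to Cohort 3; the Cohort 3 text, read literally, requires a DLT in Cohort 2. Both cannot be right. The figure of 22 is the no-DLT path through Cohorts 1 to 4, so the Cohort 2 rule is taken as intended and the entry sentence as lacking a *no*.

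**Routes to the final daily x5 dose.**

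| Route | Final dose | Tested on that route? |
|---|---|---|
| 1,200 fails | 600 | No |
| 1,200 at 1/6, then 1,700 fails | 600 | No |
| 1,200 at 0/3, then 2,300 fails | 1,700 | No |
| 1,200 at 1/6, 1,700 passes, 2,300 fails | 1,700 | Yes |
| 2,300 passes, 3,000 fails | 2,300 | Yes |
| 3,000 passes | 3,000 | Yes |

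Cohort 1's fallback of 1,700 mg/m² belongs to the Days 1 and 4 schedule and is not daily x5 evidence.

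**Evidence on the third route.** It consists of 0/3 at 1,200, with a one-sided 95% upper bound for the DLT rate of 1 − 0.05^(1/3) = 0.63, and failure at 2,300. The assigned dose is 1,700/1,200 = 1.42 times the highest cleared dose: 5 × 1,700 = 8,500 against 5 × 1,200 = 6,000 mg/m²/week.

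**How often.** The DLT rates are assumed. With rate p and q = 1 − p, a cohort passes at 0/3 with probability q³, passes at 1/6 with probability 3pq⁵, and fails with probability F(p) = 1 − q³ − 3pq⁵.

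- Untested 1,700 = q³ at 1,200 × F at 2,300.
- Final 600 = F at 1,200 + (3pq⁵ at 1,200) × F at 1,700.

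| Flat rate | q³ | 3pq⁵ | F | Untested 1,700 | Final 600, both routes |
|---|---|---|---|---|---|
| 5% | 0.8574 | 0.1161 | 0.0266 | 2.3% | 0.0266 + 0.0031 = 3.0% |
| 10% | 0.7290 | 0.1771 | 0.0939 | 6.8% | 0.09385 + 0.01663 = 11.0% |
| 20% | 0.5120 | 0.1966 | 0.2914 | 14.9% | 0.2914 + 0.0573 = 34.9% |
| 30% | 0.3430 | 0.1513 | 0.5057 | 17.4% | 0.5057 + 0.0765 = 58.2% |

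With rates of 10/20/30% at 1,200/1,700/2,300, untested 1,700 = 0.729 × 0.5057 = 37%. With 5/10/15% it is 16%.

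**The case against.** Five points can be made for the plan.

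- **The entry sentence bars the path.** Read literally it does, but it would also stop escalation after a clean Cohort 2. It contradicts the explicit 0/3 rule and the total of 22. It is a second error, not a defence.
- **1,700 is a step down from a failed dose, and patients are protected.** This stands in part. Section 6.2 requires a hold and a 25% cut for probably related Grade 2 toxicity (except alopecia and nausea), and a hold and a 50% cut for Grade 3-4. It suspends enrolment for Grade 3 or 4 acute renal failure possibly related to the drug. The Safety and Toxicity Review Committee can suspend the trial (Appendix B). Accrual of one patient a month means largely sequential treatment. Exceeding 6,000 mg/m²/week is not peculiar to this fallback either, since Cohorts 3 and 4 plan 11,500 and 15,000. A reader might infer that 1,700 is unsafe or that the ten are unprotected; the documents support neither. What is missing is the cohort-level check before ten patients are committed.
- **The scheme was discussed with or proposed by the FDA (Section 9.0).** That deserves weight, but no reason is given for this fallback.
- **Dropping to 1,200 may under-dose the response-rate sample.** This stands, and is why the fix offers a tested 1,700 as an alternative.
- **The probabilities are invented.** They are illustrative only, and flat rates across doses are not very plausible. It is tempting to multiply 37% by the 29% chance that a dose with a 20% DLT rate fails the rule, and to say that about 11% of trials would use a 1,700 that should have been rejected. That rests wholly on assumed rates. A 20% rate lies between the passing 1/6 and the failing 2/6, so such a rejection is as much small-cohort noise as evidence of harm.

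**Conclusion.** The point holds on the text and needs no assumed rate: on one conditional branch, the fallback rule gives the final ten patients a daily x5 dose that skipped the plan's own DLT check. It does not follow that the trial will reach that branch, since 1,700 is tested whenever Sub-Cohort 2 has run. Under the assumed rates above, the branch arises in 2.3% to 37% of trials.

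The 600 fallback is a separate, lesser matter. It is cautious, and its stated basis is that it equals 3,000 mg/m² per week, so a reader who sees a safety problem there goes further than the documents allow. The dose is simply not shown to be the MTD. Only after Sub-Cohort 2 fails does 600 lie below a dose that passed (1,200 at 1/6); when Cohort 2 itself fails, nothing has passed.

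**What to change.** Amend Section 6.1.1 and the copies in Section 9.0.

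1. If Cohort 3 fails and Sub-Cohort 2 has not run, choose one of two rules. (a) Open Sub-Cohort 2 at 1,700; use 1,700 in Cohort 5 only if it passes, otherwise 1,200. Its activation sentence must be widened and its exit in this case set to Cohort 5. (b) Fall back directly to 1,200. Keep 1,700 where Sub-Cohort 2 has already passed.
2. Reword Cohort 3 entry so that it opens only if none of the three Cohort 2 patients had a DLT, or at most one Sub-Cohort 2 patient did.
3. In Section 9.0, describe the ten as treated at the selected dose. Use MTD only if that Pre-Cycle 1 dose passed the DLT rule and the next higher planned dose failed it. This excludes 600 on both routes, 1,200 under option (b), and 3,000 if it passes.

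Cost: one amendment. Option (a) adds three to six patients, or as few as two if it stops early. The path maximum rises from 6+3+6+10 = 25 to 31, within the stated 40. At one patient a month, 31 months exceeds the two-year expectation, though 25 already does. Option (b) adds no patients but may under-dose the response-rate sample. Items 2 and 3 are wording changes.
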